# Guidelines for Preparing a Research Protocol

#### Instructions:

- You do not need to complete this document if you are submitting an *Application for Exemption* or *Application for a Chart Review*.
- Do not use this template if:
  - Your study involves an FDA regulated product. In this case, use the *Clinical Trial Protocol Template*.
  - Your study has a protocol from a sponsor or cooperative group. In this case, use the *Protocol Plus*.
  - Your study is a registry or repository for data and/or samples, In this case, use \*Protocol Template - Registry Studies.\* .
- If a section of this protocol is not applicable, please indicate such.
- Do not delete any of the text contained within this document.
- Please make sure to keep an electronic copy of this document. You will need to use it, if you make modifications in the future.
- Start by entering study information into the table above, according to these rules:
  - o Protocol Title: Include the full protocol title as listed on the application.
  - o Investigator: include the principal investigator's name as listed on the application form
  - o Date Revised: Indicate the date at which the protocol was last revised
  - o IRB Number: Indicate the assigned IRB number, when known. At initial submission, this row will be left blank.
- Once the table information in entered, proceed to page 2 and complete the rest of the form.

 $oldsymbol{\psi}$  Continue to next page to begin entering information about this study  $oldsymbol{\psi}$ 

Version Date: 2/26/16 Page 1 of 25

Version Date: 2/26/16 Page 2 of 25

#### 1. PREVIOUS STUDY HISTORY

Has this study	y ever been re	eviewed an	d rejected/	disapproved	by a	nother	IRB	prior	to
submission to	this IRB?								

$\boxtimes$	Nο	Yes –	if ves	nlease	explain
$L \Lambda$	110	1 05	II y co,	prease	слрішіі.

# 2. BRIEF SUMMARY OF RESEARCH

- The summary should be written in language intelligible to a moderately educated, non-scientific layperson.
- It should contain a clear statement of the rationale and hypothesis of your study, a concise description of the methodology, with an emphasis on what will happen to the subjects, and a discussion of the results.
- This section should be ½ page

It is common to have voiding difficulties after prolapse and incontinence surgeries. Difficulties in voiding are seen in up to 47% of patients after transvaginal prolapse surgery in the immediate hours postoperatively. Accepted protocols for voiding trials after prolapse and incontinence surgeries do not exist. Traditionally, many surgeons measure postvoid residual (PVR) urine volume to assess incomplete bladder emptying by retrograde filling of the bladder with a predetermined amount of normal saline or water. The catheter is then removed and the patient is permitted to void into a collection basin. The amount in the basin is subtracted from the filled amount. The need for postoperative catheterization is generally based on arbitrarily determined ratios of voided urine to PVR. The force of stream trial (FAST) does not prioritize amount voided, but rather the patient's subjective force of stream. Using FAST, a patient uses a VAS scale to quantify her force of stream. If she states that her Force of Stream (FOS) is >50% of her baseline prior to surgery, independent of the amount voided, she is discharged without a catheter. If the FOS is <50%, a PVR is measured via bladder scan. If her PVR is <500cc the patient is discharged home. No randomized control trials (RCT) have been performed comparing the FAST method to the traditional retrograde voiding trial in subjects undergoing vaginal apex prolapse surgery despite the promising findings that FAST voiding trials are as reliable and safe as retrograde voiding trials in patients undergoing anti-incontinence surgeries. Standard in our practice is to perform a voiding trial on postopeartive day 1 on all patients after vaginal apical prolapse surgery if they are to be discharged without a catheter. We would like to compare the FAST voiding trial to a traditional retrograde voiding trial with respect to the rate of catheterization among those discharged without a catheter within the six-week postoperative period in patients undergoing a vaginal apex prolapse surgery. We hypothesize the FAST voiding trial method is not inferior to traditional retrograde voiding trial. Subjects will complete questionnaires to examine postoperative bladder function, symptom distress and quality of life before and after surgery during their routine postoperative visits. We anticipate to find no difference in rates of catheterization in those discharged without a catheter in the 6-week postoperative period, the rate of urinary tract infection, the number of emergency room or unplanned office visits for voiding dysfunction or urinary tract infections, or a difference in urinary symptom scores using the questionnaires.

Version Date: 2/26/16 Page 3 of 25

# 3. INTRODUCTION/BACKGROUND MATERIAL/PRELIMINARY STUDIES AND SIGNIFICANCE

- Describe and provide the results of previous work by yourself or others, including animal studies, laboratory studies, pilot studies, pre-clinical and/or clinical studies involving the compound or device to be studied.
- Include information as to why you are conducting the study and how the study differs from what has been previously researched, including what the knowledge gaps are.
- Describe the importance of the knowledge expected to result

The acceptable amount voided urine during the traditional retrograde voiding trial varies among practitioners. In a study by Kleeman et al, the patient was required to void >50% of volume filled during retrograde fill for discharge from hospital without an indwelling Foley catheter. Pulvino et al, required that the patient void > 2/3 the amount of the volume placed during retrograde fill. The force of stream trial (FAST) does not prioritize amount voided, but rather the patient's subjective force of stream.

A double-blinded randomized trial was performed to compare retrograde bladder filling versus FAST in 108 patients undergoing outpatient midurethral sling surgery. Authors defined passing the retrograde filling test with voiding at least two-thirds of the instilled amount whereas passing the FAST method required the subject to disclose a FOS at least 50% of the baseline regardless of the volume voided. No differences were found between incidence of catheterization between the two groups (retrograde 25.5%, force of stress 26%; p=0.95) and no differences in urinary symptom and distress scores and pain scores on questionnaires given postoperatively. Importantly, no patients who passed either the FOS or retrograde fill tests required catheter reinsertion within 6 weeks postoperatively. The authors concluded the FAST test is a reliable and safe method of testing for voiding dysfunction after midurethral sling surgery.

Temporary catheterization does not pose a significant medical risk, but it is perceived as an inconvenience, a source of discomfort, and may be distressing for many patients. Elkadry et al. evaluated patient perception on surgical outcomes and concluded that 9% of women believed postoperative catheterization to be a surgical complication 12. In addition to the distress and incontinence a catheter poses on a patient, resources and time must be spent in teaching proper care of an indwelling Foley catheter by nursing or housestaff. No randomized control trials (RCT) have been performed comparing the FAST method to the traditional retrograde voiding trial in subjects undergoing vaginal apex prolapse surgery despite the promising findings that FAST voiding trials are as reliable and safe as retrograde voiding trials in patients undergoing anti-incontinence surgeries.

# 4. OBJECTIVE(S)/SPECIFIC AIMS AND HYPOTHESES

- A concise statement of the goal(s) of the current study.
- *The rationale for and specific objectives of the study.*
- The goals and the hypothesis to be tested should be stated.

We would like to compare the FAST voiding trial to a traditional retrograde voiding trial with respect to the rate of catheterization among those discharged without a catheter within the six-week postoperative period in patients undergoing a vaginal apex suspension surgery. In addition we aim to identify the number of patients sent home with a catheter due to failure of their respective voiding trial, the rate of reported urinary tract infections, the rate of unexpected or emergent visits for voiding dysfunction or urinary infections, the time from passing the voiding trial to catheterization within the 6-week postoperative period, and the degree of urinary symptoms and impact on quality of life in the postoperative period.

Version Date: 2/26/16 Page 4 of 25

#### 5. RESOURCES AVAILABLE TO CONDUCT THE HUMAN RESEARCH

- Explain the feasibility of meeting recruitment goals of this project and demonstrate a potential for recruiting the required number of suitable subjects within the agreed recruitment period
  - How many potential subjects do you have access to?
- Describe your process to ensure that all persons assisting with the trial are adequately informed about the protocol and their trial related duties and functions

Our division performs approximately 200 vaginal apex suspension surgeries for pelvic organ prolapse in a 12-month period. It is standard of care in our practice that all patients after vaginal apical prolpase surgery must complete a voiding trial on postoperative day 1 if they are to be discharged without a catheter. We assess postoperative voiding function using the traditional retrograde fill with 300cc saline or water postoperative day 1 prior to discharge. We also require a 2/3 quantity voided for discontinuation of catheter. The availability of potential subjects who meet eligibility criteria for this study is adequate for completion in 12 month period. All co-investigators are fellows or attending faculty in the division of urogynecology who are able to screen and approach subjects for enrollment. All are well versed in voiding trial management and protocol adherence.

# 6. RECRUITMENT METHODS

- *Describe the source of potential subjects*
- Describe the methods that will be used to identify potential subjects
- Describe any materials that will be used to recruit subjects. A copy of any advertisements (flyers, radio scripts, etc.) should be submitted along with the protocol.
- If monetary compensation is to be offered, this should be indicated in the protocol

The study population will be patients of the Urogynecology practice of Northwell Health System who are scheduled for surgery for vaginal apical prolapse with or without concomitant midurethral sling, anterior or posterior colporrhaphy. Patients will be randomized to one of two methods of voiding trial. Randomization will be stratified by site of surgery (Long Island Jewish Hospital or North Shore University Hospital) as well as type of surgery (apical vaginal prolapse surgery with a sling or apical vaginal prolapse surgery without a sling. All subjects over 18 years of age will be screened for eligibility relative to the patient inclusion and exclusion criteria. Recruitment for the study will be done via direct contact from our patient population. If a subject is found to be eligible to participate, an approved study investigator will approach her during her scheduled preoperative visit or in the hospital prior to her surgery. No form of advertisement will be used. The recruitment methods used will provide equitable selection of subjects. No forms of monetary compensation will be provided. Patients who are scheduled to have a surgery for vaginal apical prolapse with or without midurethral sling and with or without anterior and/or posterior colporrhaphy will be approached for study enrollment. Surgical procedures intended for treatment of vaginal apical prolapse are: uterosacral vaginal vault suspension, abdominal sacral colpopexy, colpocleisis, and sacrospinous ligament fixation. After informed consent is obtained, patients will be asked to complete the Urinary Distress Inventory (UDI-6), American Urological Association Symptom Score (AUASS) at the time of consent. The patient will be randomized to the FAST or traditional retrograde fill voiding trial.

Version Date: 2/26/16 Page 5 of 25

# 7. ELIGIBILITY CRITERIA

- Describe the characteristics of the subject population, including their anticipated number, age, ranges, sex, ethnic background, and health status. Identify the criteria for inclusion or exclusion of any subpopulation.
- Explain the rationale for the involvement of special classes of subjects, such as fetuses, pregnant women, children, prisoners or other institutionalized individuals, or others who are likely to be vulnerable. You cannot include these populations in your research, unless you indicate such in the protocol
- Similarly, detail exclusionary criteria: age limits, special populations (minors, pregnant women, decisionally impaired), use of concomitant medications, subjects with other diseases, severity of illness, etc.

All subjects over 18 years of age will be screened for eligibility relative to the patient inclusion and exclusion criteria. Our subject population comprises of women, ages range 18-95, various stages of physical health, who suffer from pelvic organ prolapse. The subjects have chosen, in consultation with their physician, to undergo surgery to correct their pelvic organ prolapse. It is standard of care in our practice for patients to have a medical evaluation and clearance by their internist prior to surgery to determine if patient is safe to undergo surgery. Subjects will be excluded if any of the following apply:

- 1. Patients who underwent a surgery that requires long term catheterization (i.e fistula repair or urethral diverticulum)
- 2. Patients who sustained a cystotomy during surgery as our divisional protocol is to send these patients home with a Foley catheter for 5-14 days without a voiding trial
- 3. Patients with baseline urinary retention and the inability to urinate without catheterization
- 4. Pregnant women

#### 8. NUMBER OF SUBJECTS

- Indicate the total number of subjects to be accrued locally. If applicable, distinguish between the number of subjects who are expected to be pre-screened, enrolled (consent obtained), randomized and complete the research procedures.
- If your study includes different cohorts, include the total number of subjects in each cohort.
- If this is multisite study, include total number of subjects across all sites.

The proposed sample size for this one year study is a total of 154 evaluable subjects (n=77 randomized to each voiding group). A subject will be "evaluable" if she gets randomized and is able to undergo the voiding trial. A subject who is not able to undergo the voiding trial is considered "not evaluable" and would not be included in the analysis.

Version Date: 2/26/16 Page 6 of 25

# 9. STUDY TIMELINES

- Describe the duration of an individuals participation in the study
- Describe the duration anticipated to enroll all study subjects
- *The estimated date of study completion*

This study will be conducted over 12-month period. Given our availability of potential subjects in our practice, enrollment will be completed in a timely fashion.

#### 10. ENDPOINTS

- Describe the primary and secondary study endpoints
- Describe any primary or secondary safety endpoints

#### **Primary:**

The primary outcome variable of interest is the rate of catheterization within the six-week post-operative period following surgical repair of POP, among those discharged without a urinary catheter.

# Secondary:

- 1. Proportion of patients discharged with a catheter (this is essentially the proportion of patients who failed the voiding trial)
- 2. Proportion of patients who reported *any* UTI within the six-week post-operative period. The number of UTIs reported by each patient during that period will also be recorded.
- 3. Proportion of patients with emergency room visits or unexpected visits to the Urogynecology clinic for voiding dysfunction or suspected infection, within the sixweek post-operative period. The number of ER visits or unexpected clinic visits will also be recorded.
- 4. Time-to-catheterization post-discharge: This is the number of days from discharge to catheterization (within the 6-week period post-surgery). Subjects who are not catheterized by the end of the follow-up period will be considered 'censored'.
- 5. Patient satisfaction with postoperative bladder function (measured at baseline, 2-weeks post-op and 6 weeks post-op) using:
  - a. American Urological Association Symptom Score (AUASS)
  - b. Urinary Distress Inventory (UDI-6)

# 11. RESEARCH PROCEDURES

- Include a detailed description of all procedures to be performed on the research subject and the schedule for each procedure.
- *Include any screening procedures for eligibility and/or baseline diagnostic tests*
- Include procedures being performed to monitor subjects for safety or minimize risks
- *Include information about drug washout periods*
- If drugs or biologics are being administered provide information on dosing and route of administration
- Clearly indicate which procedures are only being conducted for research purposes.
- If any specimens will be used for this research, explain whether they are being collected specifically for research purposes.
- Describe any source records that will be used to collect data about subjects

Version Date: 2/26/16 Page 7 of 25

# • *Indicate the data to be collected, including long term follow-up*

Patients who are scheduled to have a surgery for vaginal apical prolapse with or without midurethral sling and with or without anterior and/or posterior colporrhaphy will be approached for study enrollment. Surgical procedures intended for treatment of vaginal apical prolapse are: uterosacral vaginal vault suspension, abdominal sacral colpopexy, colpocleisis, and sacrospinous ligament fixation. Patients will be asked to complete the Urinary Distress Inventory (UDI-6), American Urological Association Symptom Score (AUASS) at the time of consent. After informed consent is obtained for participation in our study, the patient will be randomized to the FAST or traditional retrograde fill voiding trial as delineated below. After their surgery, the morning of postoperative day 1, one of these methods to assess voiding dysfunction/urinary retention will be performed.

# Retrograde fill voiding trial:

- Bladder drained using indwelling foley catheter placed in OR at completion of surgery
- Using the foley tubing the bladder is actively filled with 300cc normal saline or water
- The catheter tubing is removed
- The patient is instructed to void within 20 minutes
- The patient will subjectively quantify their FOS via VAS scale. However this information will not be used clinically
- If the patient has voided >2/3 (>200cc), she will be discharged without a foley
- If the patient voids <2/3 (<200cc) the amount instilled, she will be discharged home with a
  catheter, receive appropriate teaching for at-home maintenance of catheter and
  instructed to return to the office in 2-7 days in our office for a repeat retrograde voiding
  trial

- If the patient is unable to void at all, an indwelling foley catheter will be placed and she will follow up in 2-7 days in our office for a repeat retrograde voiding trial

### For the FAST voiding trial the method will be:

- Bladder drained with indwelling foley catheter that was placed in OR at time of surgery
- Catheter bag removed and bladder then retrograde filled with 300cc normal saline or water
- The catheter is deflated and removed
- Patient is instructed to void within 20 minutes from time of completion of retrograde fill to void. 20 minutes is standard of care for the time alloted for a patient to void. Independent of bladder capacity, the average person will feel the urge to void at 150-200cc and will feel fullness and the urge to void at 300cc. If a patient does not feel the urge to void after 20 minutes, she will be discharged home with a catheter secondary to voiding dysfunction. She will receive appropriate teaching for at-home maintenance of catheter and instructed to return to the office in 2-7 days in our office for a repeat retrograde voiding trial
- The patient will subjectively quantify their FOS via VAS scale. If VAS scale ≥50 (equalling ≥50%) then the catheter will remain out and no PVR will be measured
- If the VAS scale is from 0-49 (equalling 0-49%)
  - o a PVR will be checked via bladder scan (bladder ultrasound)
  - PVR is <500 the patient will be discharged WITHOUT a catheter

  - o PVR is >500 the patient will be discharged WITH a catheter
- If the patient is discharge with an indwelling foley catheter, she will follow up in 2-7 days in our office for a repeat test with a retrograde voiding trial, which is routine practice in our office

Prior to retrograde fill, the bladder is drained by adjusting the foley catheter in situ. It is important to note that complete drainage of the bladder is not always possible as the catheter may become kinked during emptying or blocked from collapsed bladder tissue. After

Version Date: 2/26/16 Page 8 of 25

adequate drainage, 300 cc saline or water is instilled into the bladder during retrograde fill.

In addition, intraoperatively, patients receive >1000cc fluid as well as 125 cc/hr of maintenance fluid. On average patients will make 50-100cc of urine an hour. Taking these clinical scenarios under consideration is important to understand how the PVR can be higher than the 300cc instilled in the bladder during the FAST method.

Under anesthesia the bladder has a capacity ranging from 700-1000cc. Awake the bladder capacity is less, secondary to patient's urge to urinate secondary to bladder fullness which on average occurs at 300cc. The FAST voiding trial method showed that 500cc is an acceptable and safe amount in the bladder after midurethral sling placement if the patient states her FOS is >50% preoperatively.

All patients discharged with a Foley catheter will be provided with the hospital's standard teaching for home care of Foley catheter. All patients will be instructed to notify their physician if they had any postoperative problems, specifically difficult voiding, or signs or symptoms of infection. All patients will be scheduled for a follow-up visit with the surgeon at 2 weeks and at 6 weeks postoperatively. This is standard in our practice regardless of participation in the research study. At these visits, patients will have another PVR obtained by bladder scan. The UDI-6 and AUASS will be re-administered at those visits as well.

We will collect information from their outpatient electronic medical records. Information collected will include age, race, body mass index, parity, severity of prolapse preopreatively, preoperative Urodynamics (UDS) including: cough stress test, leak point pressures, Urethral pressure profiles, presence of detrusor instability, use of antiincontinence medications, surgical history, urinalysis and PVR.

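### The FAST steps have no rule for a woman who feels the urge but passes no urine; if her stream is scored 0, she can go home without a catheter

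*Combined protocol and SAP*

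**What the plan says.** Section 11 sets out the two discharge algorithms separately. Both arms receive a 300 cc fill, and the woman is told to void within 20 minutes.

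- **Retrograde arm.** Besides the two-thirds volume criterion there is a separate line for complete failure: "If the patient is unable to void at all, an indwelling foley catheter will be placed", with a return visit in 2-7 days.
- **FAST arm, 20-minute step.** The rule depends on sensation: "If a patient does not feel the urge to void after 20 minutes, she will be discharged home with a catheter".
- **FAST arm, later steps.** The woman rates her force of stream (FOS) on a VAS. At 50 or more the catheter stays out and no residual is measured. At 0-49 the bladder is scanned: "PVR is <500 the patient will be discharged WITHOUT a catheter", and a residual above 500 leads to discharge with a catheter.

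The lay summary in section 2 gives the same low-stream rule, "If her PVR is <500cc the patient is discharged home", and likewise has no line for a woman who cannot void.

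The text after the FAST steps explains how a residual can exceed the 300 cc instilled: "complete drainage of the bladder is not always possible", and "On average patients will make 50-100cc of urine an hour". It then describes 500 cc as acceptable after a midurethral sling, on condition that the woman reports a stream above 50%.

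**The concern.** A woman can have normal sensation and still be unable to pass urine. Section 11 itself says that the average person feels the urge at 150-200 cc and fullness at 300 cc, so urge is the expected state after this fill. A rule based on absence of urge therefore misses the ordinary presentation of complete retention, and the next written steps can lead to discharge without a catheter.

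Two things are at stake. One is safety: a woman in complete retention could leave hospital on postoperative day 1 undrained. The other is uniform execution: without a written rule, two staff members could handle the same woman differently. One would send her home as a FAST pass, and the other would place a catheter and record a failure.

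**Working it through.** The plan states no figure for the bladder volume of a woman who voids nothing, so there is none to reproduce. The check sets the rules side by side and then adds up volumes from the protocol's own inputs.

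**Step 1: the rules (section 11).**

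| Situation | Retrograde arm | FAST arm |
|---|---|---|
| No urge at 20 minutes | No separate line | Catheter |
| Urge present, nothing voided | Catheter | No line |
| Stream rated 0-49 | VAS recorded, not used | Scan; residual <500 means no catheter, >500 means catheter |
| Stream rated 50 or more | VAS recorded, not used | No catheter |

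**Step 2: where the FAST woman in the second row goes.** If her absent stream is scored 0, she falls in the 0-49 range and is scanned. If the VAS is treated as not ratable, no FAST rule applies to her.

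**Step 3: what the scan would show.** Inputs: 300 cc instilled; average urine output r = 50-100 cc per hour; undrained volume before the fill u, which the protocol says can occur but does not quantify. With nothing voided:

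residual = 300 + r × (minutes / 60) + u

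At 20 minutes with u = 0:

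- r = 50: 300 + 50 × 20/60 = 316.7 cc
- r = 100: 300 + 100 × 20/60 = 333.3 cc

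The undrained volume needed to reach 500 cc at 20 minutes is 500 − 316.7 = 183.3 cc or 500 − 333.3 = 166.7 cc.

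The protocol gives no scan time. At 60 minutes the residual is 350-400 cc, and 100-150 cc undrained would be enough to reach 500. If output matched the 125 cc per hour maintenance infusion (an assumed high rate), the 60-minute residual would be 300 + 125 = 425 cc. With full drainage, every one of these values is below 500.

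**Step 4: whether the cited safety support covers her.** The section 11 statement on 500 cc is conditional on a stream above 50%. In the earlier randomised sling trial described in section 3, passing FAST required a stream of at least 50% of baseline, and the absence of catheter reinsertion is reported for women who passed. Section 17 relies on that trial to expect no additional risk. A woman with no stream meets neither condition.

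**Step 5: whether such women are expected at the scan.** The protocol explains why a residual can be larger than the volume instilled. Women who retain essentially the whole fill are therefore expected to reach this step.

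**The case against.** The strongest reply is that the FAST steps run in sequence. The woman is told to void within 20 minutes, a catheter follows if that fails, and only then come the stream rating and the post-void residual, both of which presuppose a void. On that reading the 20-minute step was meant for anyone who has not voided, and the reference to urge is loose drafting. This may well be the intent. The text does not say so, however, and the retrograde steps show that the authors wrote the explicit rule where they wanted it. A reader might infer that the protocol directs staff to discharge women in complete retention. The documents do not support that: the route depends on a score of 0 that no line prescribes.

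A second reply is that investigators experienced in voiding trials (section 5) would place a catheter anyway, and that safeguards exist: "All patients will be instructed to notify their physician if they had any postoperative problems, specifically difficult voiding", residual checks at 2 and 6 weeks, and counselling with a 24-hour line (sections 17 and 18). These points stand as mitigation. But the safeguards act after discharge, and reliance on judgement does not ensure uniform handling.

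A reader might also infer that the gap biases the primary comparison, because the outcome is counted "among those discharged without a urinary catheter" and the same woman could be in the FAST denominator but never in the retrograde one. The documents do not support that as a specific threat. Women who void under 200 cc and pass FAST differ between arms in the same way; this follows from comparing two discharge rules. A non-voider sent home and later catheterised would count as a FAST event, which works against declaring non-inferiority.

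Finally, the volumes in step 3 rest on average output and an assumed scan time, so 167-183 cc undrained is not a fixed threshold. The direction stands: such a woman would typically scan below 500 cc.

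**Conclusion.** The point holds as a gap in the FAST procedure that should be fixed. It is certain that the line is missing and that the retrograde arm has one. It is inferred that an absent stream would be scored 0. Given that score, full drainage, average urine output and a scan at 20 minutes, the woman would hold about 317-333 cc, and the written rule would send her home without a catheter. The protocol's own support for the 500 cc limit does not extend to her.

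The documents give no frequency. For scale, one such woman would move the FAST proportion discharged with a catheter by 1/77 = 1.3 percentage points. The case rests on patient safety and consistent conduct. No effect on the non-inferiority conclusion is shown.

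**What to change.** Widen the 20-minute rule in the FAST steps of section 11. Suggested wording: *A woman who has no urge, or who has passed no urine at all, by 20 minutes after the fill goes home with a catheter, returns in 2-7 days for a repeat retrograde trial, and is counted as a failed FAST trial.* The existing catheter-care teaching stays.

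Women who void any amount continue to the VAS and residual steps unchanged, because disregarding the volume voided is the FAST method itself. The lay summary in section 2 need not carry this branch.

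The cost is one clause, with no extra patients, visits or tests. The trade-off is that a few more FAST women may go home with a catheter and count as failures.
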